8.1. Retrospective Data

Data collected in the clinical routine, e.g., demographics, medication intake, concomitant diseases and procedures, disease and motor severity, detailed neuropsychological assessments, and detailed non-motor symptom assessments, will be included in the data analysis. If these parameters are collected when participating in other clinical studies, these will also be included.

8.2. Neuropsychological testing

The aim is to diagnose PD-MCI and PDD according to the Level-II recommendations of the Movement Disorder Task Force [17, 18, 25]. Therefore, the following five domains will be quantitatively assessed using the Consortium to Establish a Registry for Alzheimer's Disease (CERAD-Plus) battery, three subtests of the Wechsler Intelligence Test for Adults (WIE), and one subtest of the Leistungsprüfsystem für 50- bis 90-Jährige (LPS 50+). At least two tests are assigned to each cognitive domain:

- Executive functions: Lexical and Phonemic Fluency (CERAD-Plus), Trail Making Test Part B (CERAD-Plus)
- Attention/working memory: Digit-Symbol Test (WIE), Letter-Number Sequencing (WIE)
- Language: Boston Naming Test (CERAD-Plus), Similarities (WIE)
- Memory: Word List Learning, Recall, and Discriminability (CERAD-Plus), Praxis Recall (CERAD-Plus)
- Visuospatial abilities: Praxis (CERAD-Plus), Fragmented Words (LPS-50+)

The MMSE included in the CERAD-Plus, as well as the Montreal Cognitive Assessment (MoCA) will serve as global cognitive screening scales. In addition, the DATE will be applied. The DATE by Johnen and colleagues [29] was developed to assess limb and buccofacial apraxia in neurocognitive disorder patients with Alzheimer's disease and frontotemporal dementia. Based on scores in the first follow-up, progression in the DATE performance over time will be investigated. For validation purpose, the Kölner Apraxie Screening [30] will be included as well. Patients' performance in the DATE and KAS will be videotaped for data analysis. Videotaped data will be solely used for scoring of the DATE and KAS, also including registration of patient's body parts and face. After scoring of patient's test performance and finalization of study analysis, videodata will be deleted. Only, information of patients test performances as a result of the videoanalysis will be shared with collaboration partners.

In addition, we will validate a novel scoring algorithm of patients' cube drawing (CERAD-PLUS test battery) proposed as a measure for retrograde procedural memory [31]. Therefore, investigators will be trained for this novel scoring method by the collaborating group of [name], University of Luxembourg. Patients' performance will be scored by the investigators during test session, therefore, no additional time for patients' examination is expected.

8.3. Home-based movement assessment (Accelerometer)

Physical activity directly influences health-related quality of life in PD [32], with specific aspects of physical activity decreasing with the severity of cognitive impairment [33]. We will therefore conduct a home-based movement assessment in a random subgroup of patients, to examine the influence of physical activity on cognition and other non-motor symptoms in PD. Participants will be asked to wear an accelerometer (MoveMonitor, McRoberts, The Netherlands, FDA registered and CE marked) on their lower back for 7 consecutive days in their home environment. The accelerometer is capable of data uptake for 7-10 days, and assesses various movement parameters (e.g., time spent sitting, lying, walking, and standing, as well as step count).

8.4. Caregiver IADL assessments

Caregiver assessments have a crucial role determining a diagnosis of PDD, by examining whether patients are able to care for themselves and carry out their daily activities. The Bayer Activities of Daily Living Scale (Bayer ADL) consists of 25 questions answered by the caregiver that evaluate the patient's ability to perform ADL. The Informant Questionnaire on Cognitive Decline in the Elderly (IQ-CODE), a brief screening tool for dementia, compares patients' current abilities to how they were two years ago. In addition, caregiver burden will be assessed using two questionnaires, the Parkinson's Disease Angehörigen Belastungs- und Befindlichkeitsskala (PD-ABB-Scale) and the ZARIT Caregiver Burden Inventory (ZCBI). This provides a useful marker for cognitive ADL progression, as well as helps to distinguish cognitive decline from normal aging. The caregiver assessment of ADL using the FAQ allows us to compare patient and caregiver evaluations of ADL impairments.

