Results. Of 268 patients with PD assessed at baseline, 108 (40.3%) had PD-MCI. After a period of 3.8 ± 0.8 years, 182 (61.2%) patients were re-assessed and 164 analysed (17 excluded due to deep brain stimulation, one patients without classification of cognitive group). At follow-up, 93 (56.7%) patients fulfilled criteria for normal cognitive function (PD-CN), 54 for PD-MCI (32.9%), and 17 (10.4%) had developed dementia. Predictive ratio of baseline cognitive IADL impairment (n=37; 21.3%) for dementia conversion was descriptively higher than for PD-MCI, but highest in patients with both markers [HR=12.01, 95%-confidence interval (CI): 4.47-32.23]. Nearly half of patients (n=10, 47.6%) with baseline classification of cognitive IADL impairment and PD-MCI converted to dementia. Baseline status of cognitive IADL impairment was associated with higher non-motor burden, worse cognitive performance, and more severe IADL progression over the study period. In a post-hoc Receiver Operating Characteristic (ROC) analysis, the FAQ quotient (cut-off >1.008) was confirmed to best predict conversion to dementia compared to other IADL scores. Only two patients with baseline status of cognitive IADL impairment in our sample scored below the newly identified FAQ quotient cut-off of 1.008 resulting in a total of 35 (21.3%) patients with values above this defined cut-off. The FAQ motor score [AUC(area under the curve)=0.60, 95%-CI: 0.52-0.67, $p=0.13$], reflecting predominantly motor aspects on IADL function, was not associated with PDD conversion.

4. Objectives of the study

Based on previous analyses in the sample we suggest that monitoring of both cognition and cognitive ADL impairment reflect neurodegeneration associated to PDD development. This study evaluates markers predicting cognitive and ADL long-term outcome in our sample. Additionally, we will investigate whether ratings of patients or informants best predicted decline of cognitive impairment and/or everyday function. Clinical data along with other clinical marker and biomarker status will be investigated.

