6.1. Study population

Between March 30th, 2014 and December 31th, 2017, we recruited a large cohort of 268 PD patients within the frame of the "Amyloid-Beta in cerebrospinal fluid as a risk factor for cognitive dysfunction in Parkinson's Disease" (ABC-PD, ethic protocol 686/2013B01) study. Follow-up visits were conducted between July 2018 and September 2020, all patients of the ABC-PD study were contacted for re-examination.

We propose a second follow-up of the already existing longitudinal cohort described above with a longitudinal assessment including neuropsychological in-depth endophenotyping and CSF biomarker analyses. In total 182 patients will be invited to participate in the second

follow-up assessment. If patients are not able to attend a clinical visit in-house, possibility of assessments at patients' homes shall be offered. Moreover, if patients are not able to give consent for study participation (confirmed by an independent physician), the legal guardian will be contacted to give study consent for participation. Legal guardians are defined as persons with legal care directive or lasting power of attorney. For drop-outs different reasons for drop-out will be coded (e.g. deceased, disabled, disinterested/refuse study participation, unable to reach/unknown address).

Diagnosis of cognitive impairment:

Patients were classified as PD-MCI according to Level-II Movement Disorder Society recommendations if cognitive impairment was present but did not significantly interfere with everyday function [25]. PDD was defined according to Movement Disorder Society Task Force criteria [17] if cognitive impairment was present and severe enough to impair ADL function unrelated to motor or autonomic symptoms and at least one behavioral symptom was present to support diagnosis. Cognitive impairment was defined according to Level-I (impairment of global cognition) for patients with minimal assessments, or Level-II (performance below 1.5 standard deviation of the population mean reported in the test manuals on at least two tests) for patients assessed using a full cognitive battery. Patients not meeting either of the diagnostic criteria were classified as PD-CN. Cognitive status at follow-up was defined as the primary study outcome.

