Prediction of cognitive progression along with progression in ADL function over time: In patients who completed all visits, the predictive values of baseline/follow-up IADL (patients' self-impression vs. informant-rating), stratification (cognitive IADL impairment vs. motor IADL impairment), cognitive status (PD-CN vs. PD-MCI), and both markers combined (PD-MCI + cognitive IADL impairment) will be calculated using multivariate Cox Proportional-Hazard models. Akaike's information criterion (AIC) and concordance index (C-index) [26] will be used as model fit indices. Logistic regression with follow-up cognitive diagnosis (PD-CN vs. PD-MCI or non-demented vs. PDD) as dependent variable will evaluate whether baseline status of cognitive IADL impairment (FAQ quotient >1.008) predicted risk of PDD conversion independent of other clinical variables (e.g., cognitive status), biomarker profile, and covariates. As a post-hoc exploratory analysis to identify which subscore best predicted PDD conversion, ROC curves will be calculated for all FAQ scores (self- and caregiver-assessment). The optimal score/cut-off will be chosen according to the highest Youden Index. Linear regression will be applied to investigate predictors of neuropsychological scores and IADL measures at follow-up(s).

2. Defining the interaction of progression in markers over time

Generalized linear mixed effects models (GLMMs) will evaluate progression in neuropsychological tests and IADL scores over time. Correlation analyses are planned to investigate association in change of scores over time of different measures.

Sample size calculation:

Between the baseline and first follow-up 17 (10.4%) patients developed PDD within a mean follow-up interval of 3.78 ± 0.84 years (range: 1.67-5.79 years), with higher rates of converters in patients with baseline status of cognitive ADL impairment (29.7%). Estimated follow-up interval between first and second follow-up are expected to be very similar, and a higher rate of patients with cognitive ADL impairment were identified. Moreover, the risk for PDD development is increased in later disease stages [27, 28]. Therefore, a maximum of additional 15 converters are expected.

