Monte Carlo simulation-based calculations of observed power (R package simr, version 1.0.6), revealed a minimum sample size of $n = 64$ (Power = 94.00%; 95%-CI: 83.45-98.75) to detect the three-way interaction in the GLMM evaluation of the progression in the FAQ total score in different study groups (e.g., PD-NC vs. PD-MCI), and of $n = 71$ (Power = 92.00%; 95%-CI: 80.77-97.78) for the three-way interaction in the GLMM evaluating progression of FAQ motor score.

8. Assessments

The explanation of study requirements and informed consent will be conducted as first procedure.

Table 1: Overview of clinical in-house assessments and assessments which can alternatively be assessed within an additional phone interview.

Assessment of PD patients	Time
Explanation of the study requirements	10 min
Informed written consent	5 min
Neurological assessments:	
Medication intake, concomitant diseases and procedures	10 min
Unified Parkinson's Disease Rating Scale (UPDRS) Parts III-IV, Hoehn & Yahr Stage*	15 min
Cognitive test battery:	
Montreal Cognition Assessment (MoCA)	10 min
Mini Mental State Examination (MMSE)	5 min
Consortium to Establish a Registry for Alzheimer's Disease (CERAD-Plus, German Version)	25 min
Trail Making Test Parts A and B	10 min
Fragmented Words (Subtest of the Leistungsprüfsystem für 50- bis 90-Jährige, LPS 50+)	5 min
Digit-Symbol Test (Subtest of the Wechsler Intelligenztest für Erwachsene, WIE)	5 min
Similarities (Subtest of the WIE)	5 min
Letter-Number Sequencing (Subtest of the WIE)	5 min
Pill-Questionnaire	5 min
Total time of mandatory in house assessments	115 min
Optional: Dementia Apraxia Test (DATE)	5 min
Optional: Kölner Apraxie Screening	8 min
Total maximum time of optional in house assessments	13 min
Assessments, which can be alternatively assessed within an additional phone interview	
Demographics & lifestyle	
Age, gender, education, occupation, family history of neurodegenerative diseases, smoking/drinking behavior, height & weight#	5 min
PD Non-Motor Symptom Scale, subscales 1-5 (PD-NMS-S) #	5 min
Unified Multiple System Atrophy Rating Scale (UMSARS) I: History of autonomic symptoms#	2 min
History and self-awareness of cognitive deficits#	5 min
Total maximum time of additional phone interview	17 min

Legend: *: For patients with an appointment in the outpatient clinic data will be assessed within the frame of the clinical daily routine;
#: Information can be assessed within the frame of phone interview

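### Caregiver input to the PDD diagnosis is not kept apart from the patient-versus-informant comparison of PDD predictors, which can bias that comparison towards informants

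*Combined protocol and SAP*

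**What the plan says.** The outcome: Section 6.1 defines PDD as present if "cognitive impairment was present and severe enough to impair ADL function unrelated to motor or autonomic symptoms", together with at least one supporting behavioural symptom. It adds that "Cognitive status at follow-up was defined as the primary study outcome". It names neither the instrument nor the rater that settles the ADL part.

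The source of the ADL judgement: Section 8.4 says "Caregiver assessments have a crucial role determining a diagnosis of PDD", because they show whether patients can look after themselves and manage everyday tasks. It then describes the Bayer ADL, the IQ-CODE and the caregiver FAQ. Section 8 also introduces the caregiver scales as a means of validating what patients report about themselves.

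The comparison: Section 4 states that "we will investigate whether ratings of patients or informants best predicted decline of cognitive impairment and/or everyday function". Section 7 puts this into Cox models of IADL ratings ("self-impression vs. informant-rating") taken from baseline or follow-up. It adds exploratory ROC curves of all FAQ scores, from patient and caregiver, against PDD conversion.

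The plan does not keep the caregiver scales out of the diagnosis, does not blind the diagnosing clinician to them, and plans no analysis with PDD defined without caregiver input.

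**The concern.** If a caregiver's report helps decide who is labelled PDD, that caregiver's rating is being compared with something it partly produced. The patient's rating has no stated equivalent role. A better C-index or AUC for informants could then mean that they know more, or only that they helped set the outcome, and the planned analysis cannot tell these apart.

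The effect is direct if the rating comes from the visit at which PDD is diagnosed. For an earlier rating it needs a rater-specific tendency that lasts from one visit to the next, such as a caregiver who is consistently strict. Section 3.1 reports only moderate patient-informant agreement on FAQ items in this cohort, and ratings related to characteristics other than cognition. Rater-specific variation is therefore plausible, but the documents do not show how stable it is.

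At stake is a stated objective, which Section 3.1 gives as a reason for the second follow-up.

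**Working it through.** The plan gives no AUC, C-index, sample size or power for the rater comparison, so there is no figure to reproduce. Its power statements concern FAQ progression in mixed models. The check below shows direction and plausible range only.

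**Inputs from the documents.** PDD by first follow-up: 17/164 = 10.4% (Sections 3.2 and 7). At most 15 further converters (Section 7) among 145 patients (Section 6.3): 15/145 = 10.3%. A rough cumulative rate is 10.4% + 10.3% = 20.7%.

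**Assumptions not in the documents.** Reliability of each rating 0.6; correlation of true ADL deficit between visits 0.7; correlation of cognition with true deficit 0.6; stable share of rater error s = 0, 0.3 or 0.6; informant weight in the ADL judgement w = 0, 0.5 or 1.

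**Model**, 400,000 simulated patients per scenario:

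- True deficit: T1 = 0.7·T0 + √0.51·e
- Rating by either rater at visit t: √0.6·Tt + √0.4·(√s·b + √(1−s)·e), where b is that rater's lasting tendency. Patient and informant have identical validity.
- Examiner's view: √0.6·T1 + √0.4·e
- ADL judgement: J = w·(informant rating at diagnosis) + (1−w)·(examiner's view)
- Cognition: C = 0.6·T1 + 0.8·e
- PDD: the highest 10.4% or 20.7% of J/SD(J) + C

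**AUC, informant minus patient:**

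| PDD rate | s | w | Earlier-visit rating | Diagnostic-visit rating |
|---|---|---|---|---|
| 10.4% | 0 | 0.5 | 0.747 − 0.747 = 0.000 | 0.908 − 0.848 = 0.060 |
| 10.4% | 0 | 1 | 0.737 − 0.736 = 0.001 | 0.943 − 0.833 = 0.110 |
| 10.4% | 0.3 | 0.5 | 0.767 − 0.747 = 0.020 | 0.908 − 0.847 = 0.061 |
| 10.4% | 0.3 | 1 | 0.770 − 0.735 = 0.035 | 0.943 − 0.831 = 0.112 |
| 10.4% | 0.6 | 0.5 | 0.785 − 0.746 = 0.039 | 0.908 − 0.847 = 0.061 |
| 10.4% | 0.6 | 1 | 0.808 − 0.735 = 0.073 | 0.943 − 0.833 = 0.110 |
| 20.7% | 0.6 | 0.5 | 0.763 − 0.726 = 0.037 | 0.886 − 0.822 = 0.064 |
| 20.7% | 0.6 | 1 | 0.785 − 0.714 = 0.071 | 0.927 − 0.808 = 0.119 |

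With w = 0, the two AUCs agree within 0.002 in every scenario, so the gap comes from the informant's part in the outcome. If patient and informant reports enter the diagnosis with equal weight, the model is symmetric in the two raters and the expected gap is zero at either visit.

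**The case against.** Four points on the other side have force.

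1. **The source of the criterion is open.** A reader might infer that the caregiver FAQ, or the informant alone, decides PDD. The documents do not say so. Section 8.4 gives the caregiver FAQ the separate purpose of comparing the two raters' evaluations, and self-report may also feed the diagnosis. In a separate simulation (18% PDD, rater-tendency variance 0.25 to 0.5 times the true variance), weights of 0.5 for the informant and 0.25 for self-report gave an earlier-visit gap of only 0.012 to 0.021.

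2. **The same caregiver is not guaranteed.** Section 11.3 lets the patient choose the caregiver and does not require the earlier one, and the interval is about 3.8 years. In that same simulation with informant weight 1, a change of informant in 40% of cases lowered the gap from 0.040 to 0.024 and from 0.073 to 0.044.

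3. **A single headline figure is not supported.** A gap of 0.04 to 0.10 can be produced (0.733 − 0.697 = 0.036 up to 0.757 − 0.655 = 0.102). That assumes the informant alone sets the criterion, the rater tendency is wholly stable, and its variance is up to that of the true deficit. It describes an extreme case.

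4. **The objective is wider than PDD.** Aim 1.2 and the linear regressions in Section 7 already cover cognitive scales as outcomes, and the ROC step is labelled exploratory. The whole rater objective is therefore not invalid. However, the cognition-only analyses are not set out as a patient-versus-informant comparison.

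These points limit the size and reach of the bias. They do not supply the missing separation, and the first shows why the ADL source needs to be stated.

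**Conclusion.** The concern holds for the PDD-based rater comparison. Followed as written, the plan lets caregiver information shape the outcome and compete to predict it, and this can favour the informant.

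The size cannot be derived from the documents. Under the assumptions shown, the spurious AUC advantage for earlier-visit ratings runs from 0 to about 0.07. It is 0 if rater error is independent between visits or if both raters weigh equally in the diagnosis. For ratings from the diagnostic visit it is about 0.06 to 0.12 with informant weight 0.5 to 1 and no self-report in the diagnosis. Apart from simulation noise of up to 0.002, no scenario favoured the patient.

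The documents do not establish that a bias of any particular size will occur, only that the plan does not prevent one. An informant advantage for PDD would therefore be hard to interpret. The point deserves a change to the plan but does not undermine the study as a whole.

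**What to change.** 1. In Section 7, use only IADL ratings from visits before the one at which PDD is diagnosed: baseline ratings for first-follow-up converters, and baseline or first-follow-up ratings for later converters. This removes the direct route but not a lasting rater tendency, so step 2 is still needed.

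2. Run the patient-versus-informant comparison explicitly on a cognition-only outcome, either Level-II battery impairment or MoCA decline, as an extension of Aim 1.2. Draw the conclusion about which rater predicts better from that analysis, and report the PDD-based comparison as subject to incorporation bias.

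3. In Section 6.1 or 8.4, state which source sets the ADL criterion for PDD. For new diagnoses, where feasible, set it without using either version of the FAQ.

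Steps 1 and 2 need no new assessments, only a little more analysis. Step 3 affects at most the 15 further converters expected. Blinded reclassification of the 17 existing converters would be a larger task and is not proposed. The "Pill-Questionnaire" should not be assumed to be a ready-made neutral ADL source: Table 1 lists it in the cognitive battery, and the documents do not describe it as an ADL measure. The main downside is that a cognition-only outcome is not the clinical PDD diagnosis, so both results should be shown.

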8.5. Biomaterial collection

8.5.1. CSF and blood collection

Blood and CSF samples will be collected in the morning, on an empty stomach. If patients do not agree for a lumbar puncture, fasting for blood sampling is not necessary for biomarker analysis.

Blood collection: For patients with no CSF withdrawal about 40 ml venous blood will be collected for data analysis and storage of blood in the neurobank of the Hertie-Institut für klinische Hirnforschung (ethic proposal: 199/2011BO1). This amount does not represent any health hazard. For study related analysis of serum neurofilament light chain 10 ml of venous blood (1 Serum tube) will be collected. If the patient agrees for withdrawal of CSF additional 12,5 ml venous blood (2 serum tube, 1 NaF (glucose) 2,5 ml, total amount of venous blood 52,5 ml) will be taken for safety analysis in the Zentrallabor of the UKT.

Through venipuncture, the following samples will remain in the Hertie-Institut für klinische Hirnforschung (ethic proposal: 199/2011BO1):

- 20 ml of venous blood in 2 large EDTA tubes
- 10 ml of venous blood in 1 Serum tube

Blood in the Neurobiobank will be stored and used for targeted biomarker search, for explorative proteomic and metabolomics approaches, as well as for the determination of genetic markers in those without DNA analysis by using the NeuroChip (e.g. APOE Genotype, MAPT, COMT, and GBA).

CSF collection: The lumbar puncture at level L3/L4 or L4/L5 of the spine will be performed by a qualified clinician. The applicants have extensive experience with this procedure (see, e.g., ethic proposals 46/2010 and 404/2010). Subjects will be closely monitored during and after the procedure. Patients need to rest for 30 min after CSF collection and will be informed that occurrence of side effects of this procedure might be interfere with their driving abilities. Up to 15 ml of CSF will be collected unless there is evidence of clinically significant coagulopathy or thrombocytopenia that would interfere with the safe conduct of the procedure. This amount does not represent any health hazard. The first 2 ml of CSF will be processed at the Zentrallabor to conduct standard analyses on cell count, protein, and glucose levels, while another aliquot of 400 µL Liquor will be sent to the Neurochemisches Labor to conduct analyses of neurodegenerative markers such as Abeta1-42 and Abeta1-40.

8.5.2. *Tissue collection*

Not applicable.

8.5.3. *Analysis of biomaterial*

A structured and integrated exploration of biomaterial in combination with the analysis of the extensive quantitative dataset obtained in this study bears the chance for a better molecular, biochemical, and eventually functional understanding of one of the most debilitating symptoms associated with PD, i.e., cognitive deterioration.

For all patients, DNA, CSF, and plasma were sampled at baseline. Available data will be included into data analysis. This includes genetic information received from DNA analysis by using the NeuroChip, especially information on genetic variants associated with dementia and PD, as well as CSF levels of Abeta1-42, phosphor- and total Tau determined within the frame of the ABC-PD study. In collaboration with the company ADX, represented by [name] and [name], the following baseline CSF biomarkers were provided for further analysis of 200 patients: Abeta1-42, Abeta1-40, Abeta1-38, phosphor Tau 181, NF heavy, neurogranin, BASE-1, and alpha-synuclein.

At time of follow-up, a maximum of 50 PD patients is expected to give a third CSF sampling. Levels of CSF biomarkers indicating cognitive worsening [8, 9, 34-37] will be measured using the solid phase enzyme essays from Fujirebio Germany GmbH: Abeta1-42, Abeta1-40, phosphor- and total Tau. In addition, blood (serum) neurofilament light chain will be analysed in cooperation with [name]. med. [name] of the Universitätsklinikum Dresden.

8.5.4. *Storage of biomaterial*

All samples will be stored at -80°C until use. To maximize confidentiality, all biomarker samples and information associated with the samples will be coded to prevent the exposure of the subjects' information and identity. This coding process allows location and destruction of a sample at the subject's request. In addition, sample information is stored in one secured

electronic database, while biomarker data is stored in an independently secured database on a different computer. No one except the investigators of the UKT will have access to the database to deduce the identity of the patient.

9. Risks and possible adverse reactions, end of the study

